## 5. INTRODUCTION

### 5.1. Background

Hereditary angioedema (HAE) is an autosomal dominant disorder characterized by recurrent episodes of swelling of the skin, pharynx, larynx, gastrointestinal tract, genitals, and extremities (Longhurst and Cicardi 2012). The frequency of attacks varies between subjects, from rarely in some patients to every few days in others. Angioedema attacks may or may not be precipitated by a stimulus (such as stress, trauma, or estrogen) and are typically rapid in onset, with symptoms subsiding gradually over the following 3 to 5 days (Zuraw and Christiansen 2011). Oropharyngeal swelling can be life-threatening (Bork, Hardt et al. 2012), while attacks in other sites, including limbs, genitalia, face and intestines, can be painful, disabling, and disfiguring, and have a significant impact on functionality and quality of life (Lumry, Castaldo et al. 2010). Although mortality risk from asphyxiation is much higher in undiagnosed patients with HAE, deaths still occur in diagnosed patients with access to care at centers of excellence (Bork, Hardt et al. 2012).

Extensive evidence from animal models and clinical studies supports the role of bradykinin (BK) as the principal mediator of the signs and symptoms that characterize attacks of HAE (Kaplan 2010, Zuraw and Christiansen 2011). Plasma kallikrein is a serine protease integral to the contact activation pathway (Saxena, Thompson et al. 2011). Kallikrein circulates in plasma as a zymogen, prekallikrein (PKK), bound to one of its main substrates, high-molecular-weight kininogen (HK). During contact activation, PKK is cleaved by activated factor XII, forming the active protease kallikrein. Kallikrein in turn cleaves HK, producing BK (Kaplan and Ghebrehiwet 2010). The activation of the bradykinin B2 receptor by BK ultimately results in vasodilatation, increased vascular permeability, and smooth muscle contraction, all of which lead to the tissue swelling that characterizes HAE (Kaplan 2010).

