#### **10.8. Derived Attack Endpoints**

Subject-reported attacks will be adjudicated by the independent Clinical Endpoint Adjudication Panel (CEAP). The attacks that have been confirmed by the adjudication committee will be included in efficacy analyses. The details of adjudication are provided in the CEAP charter.

The attack endpoints described in this section are based on confirmed attacks by the CEAP, however the rate of attacks will also be calculated for all subject reported attacks. Efficacy analyses will be conducted for HAE attacks reported over the entire dosing period (Days 1 to 28

inclusive), during the dosing period in which BCX7353 should be at steady-state conditions (Days 8 to 28, inclusive), and during the entire study period (Day 1 to the last HAE diary in the follow-up period).

The efficacy analyses will be calculated for 3 treatment periods:

- Entire Dosing Period  
Duration (days) = 28 or (Date of last dose –date of first dose+1), whichever is earlier
- Effective Dosing Period  
Duration (days) = 21 or (Date of last dose –date of first dose-6), whichever is earlier
- Entire Study Period  
Duration (days) = Date of last HAE Attack Diary collection during the follow-up –date of first dose

All efficacy analyses will also be run by treatment period and population (FAS or PP).

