#### 12.1.4. Analysis of Secondary Efficacy Endpoints

The number and percentage of attack-free days will be analyzed similarly to the attack rate endpoint. The secondary efficacy endpoints including attack location, duration, symptoms of attacks, and number and percent of attacks requiring attack medication will be summarized for each treatment group.

The between-treatment comparisons for the weekly attack rate will be also be performed separately by attack location (peripheral or abdominal) using the ANCOVA model as described for the primary endpoint.

The attack onset relative to the time of last dose of study drug, discontinuations due to lack of efficacy and number of emergency room visits and/or hospitalizations will also be reported by treatment group.

AAS will be summarized descriptively by treatment group for each AAS question at attack level and at subject level. The most severe response from all confirmed attacks will be used at subject level summary. The between treatment group comparisons for the total AAS score and individual AAS question scores will be performed using an ANCOVA model. The adjusted qualifying attack rate will be included as a covariate.

The following additional efficacy analyses will also be performed:

- The attack rate in the pre and post treatment periods
- Time intervals between attacks

Time intervals between attacks will be derived as follows:

Subjects with no attack: Interval = duration of treatment or 28  
Subjects with 1 attack: Interval = the Max of the duration of (the first dose to start of the attack) or (stop of attack to the end of the dose )

Subjects with >1 attack: Interval = the duration between the stop of the first attack and start of the next attack (subjects with N attacks will have n-1 intervals)

- Time to first attack after the study medication

The time to first attack after the first study medication will be summarized descriptively and graphically using Kaplan-Meier method. The Kaplan-Meier (KM) estimate for the median, and the first and third quartiles will be determined along with approximate 95% confidence intervals. Brookmeyer-Crowley method will be used for the confidence interval calculation. Subjects who do not have an attack will be censored at the date of last dose for the KM analysis.

- Time to first attack after the last dose

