14.2.3.1.1	Summary of Time intervals between Attacks	FAS/PP
14.2.3.2	Summary of AAS Categorical Response -Attack level	FAS/PP
14.2.3.3	Summary of AAS Categorical Response -Subject level (worst response for each AAS question)	FAS/PP
14.2.3.4	Summary of AAS Total Score (include AAS total and Domain Total Score)	FAS/PP
14.2.3.5	Statistical Analysis of AAS Total Score (include AAS total and Domain Total Score)	FAS/PP
14.2.3.6	Summary of Attack Duration at Subject Level – Confirmed Attacks	FAS/PP
14.2.3.7	Summary of Attack Duration of All Confirmed Attacks	FAS/PP
14.2.3.8	Summary of Attack Triggers – Confirmed Attacks	FAS/PP
14.2.3.9	Summary of Attack Symptoms – Confirmed Attacks	FAS/PP
14.2.3.10	Summary of Number of Symptoms – Confirmed Attacks	FAS/PP

Tables	Title	Population
14.2.3.11	Summary of Attack Location – Confirmed Attacks	FAS/PP
14.2.3.12	Summary of Attack Onset time from the last dose– Confirmed Attacks	FAS/PP
14.2.3.13	Summary of Administrations of Acute HAE Medications – Confirmed Attacks	FAS/PP
14.2.3.14	Number and Percentage of Attacks Requiring Additional Medical Care	FAS/PP
14.2.3.15	Summary of time to treatment –Confirmed Attacks (overall, by country and by site )	FAS/PP
14.2.3.16	Time to Treatment (KM estimates)	FAS/PP
14.2.3.17	Summary of Qualifying, Screening Attack and Post Treatment HAE attack Rate	FAS/PP
14.2.3.18	Statistical Analysis of Post Treatment HAE attack Rate	FAS/PP
14.2.3.19	Time of First Attack after the First Dose (KM estimates)	FAS/PP
14.2.3.20	Time of First Attack after Last Dose (KM estimates)	FAS/PP
14.2.4.1	Summary of AeQoL scores	FAS/PP
14.2.4.2	Statistical Analysis of AeQoL Scores	FAS/PP
14.2.4.3	Correlation among AeQoL and Attack Rate	FAS/PP
14.2.4.4	Summary of DASS Severity-Rating Index Categories	FAS/PP
14.2.4.5	Summary of DASS scores	FAS/PP
14.2.4.6	Correlation among DASS Domains and Attack Rate	FAS/PP
14.2.4.7	Correlation between AeQoL and DASS Domains	FAS/PP
14.2.5.1	Statistical Analysis of DASS Scores	FAS/PP
Pharmacokinetic Analysis		
14.2.5.2	Summary of Plasma BCX7353 Concentration	PK
14.2.5.3	Summary of Derived Plasma BCX7353 Pharmacokinetic Parameters	PK
14.2.5.4	Summary of Trough BCX7353 Concentration	PK
14.2.5.5	Assessment of Dose Proportionality based on Power Model	PK
14.2.5.6	Assessment of Dose Proportionality based on ANOVA	PK
14.2.5.7	Assessment of Steady State	PK
14.2.5.8	Number and Percent of Average Ctrough above 4xEC50 and 4xEC80	PK

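### The SAP's time between attacks is derived by a different formula for none, one, and two or more attacks, so Table 14.2.3.1.1 does not show one quantity

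*SAP*

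**What the plan says.** Under the additional efficacy analyses in SAP 12.1.4, the interval is set by attack count:

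- No attack: "Subjects with no attack: Interval = duration of treatment or 28". The text does not say which of the two applies when they differ.
- One attack: "the Max of the duration of (the first dose to start of the attack) or (stop of attack to the end of the dose".
- More than one attack: "the duration between the stop of the first attack and start of the next attack", with the note that "subjects with N attacks will have n-1 intervals".

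The SAP does not say whether a subject's several intervals are averaged or whether all intervals are pooled within an arm. The result feeds Table 14.2.3.1.1, "Summary of Time intervals between Attacks", for the FAS and PP populations. No test or model is named for it. It is not among the comparisons of interest in SAP 7.2 or the secondary endpoints in SAP 2.2.2.

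**The concern.** The formula is chosen by the outcome that the table is meant to describe. The gaps at the two ends of the treatment period count at one attack, where the longer is taken, and are discarded at two or more. A second attack therefore does two things at once: it divides the attack-free time further, and it removes both end gaps from the measure. A subject who has two attacks close together and is then well for three weeks is described only by the short gap between them.

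The table is laid out by treatment arm, and a reader would take it as a single measure of how long subjects stay free of attacks. Where arms differ in attack count, they also differ in the mix of formulas, so the difference in days partly reflects that mix.

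**Working it through.** The documents state no figure that depends on this rule, so there is none to reproduce. The check applies the rule directly.

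**Inputs**
- Window T = 28 days for a completer. SAP 10.8: "Duration (days) = 28 or (Date of last dose –date of first dose+1), whichever is earlier".
- Attack length d: no planning value is given. Protocol 5.1 describes attacks "with symptoms subsiding gradually over the following 3 to 5 days". Assumed range: 0 to 5 days.
- Placement of attacks: not given. Assumed random and non-overlapping, with even spacing as the contrast.
- Several gaps in one subject: assumed to be averaged within the subject. The result for each subject is called the score below.

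**Fixed examples, d = 1**
- One attack starting at day 14: max(14, 28 − 15) = 14 days.
- Two attacks starting at days 2 and 5: 5 − 3 = 2 days. The 28 − 6 = 22 attack-free days afterwards do not count.
- Six attacks at 4-day spacing: 4 − 1 = 3 days.

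**Two against four attacks, d = 2.** Starts at days 10 and 15 score 3 days; starts at days 1, 9, 17 and 25 score 6. Under random placement a two-attack subject scores below a four-attack subject in 36% (d = 0), 30% (d = 2) and 17% (d = 5) of pairs. On average two attacks still score better than four (9.3 v 5.6 days at d = 0).

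**Expected score, random placement**
- SAP rule: 0.75(T − d) for one attack; (T − nd)/(n + 1) for n ≥ 2.
- Mean of all n + 1 gaps: (T − nd)/(n + 1) for every n.
- Longest attack-free interval: (T − nd)(1 + 1/2 + … + 1/(n + 1))/(n + 1). This is 0.75(T − d) for n = 1 and 0.611(T − 2d) for n = 2.

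Days for one attack, then two, with the drop:

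| d | SAP rule | Mean of all gaps | Longest interval |
|---|---|---|---|
| 0 | 21.0, 9.3 (56%) | 14.0, 9.3 (33%) | 21.0, 17.1 (18%) |
| 2 | 19.5, 8.0 (59%) | 13.0, 8.0 (38%) | 19.5, 14.7 (25%) |
| 5 | 17.25, 6.0 (65%) | 11.5, 6.0 (48%) | 17.25, 11.0 (36%) |

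At d = 0 the SAP scores for 0 to 4 attacks are 28, 21, 9.3, 7.0 and 5.6. The neighbouring steps are 25%, 56%, 25% and 20%, so the break lies where the formula changes.

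**Even spacing.** One attack scores (28 − d)/2 and two score (28 − 2d)/3, a drop of 33% (d = 0) to 48% (d = 5).

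**Between arms.** Simulation at the planning rates in SAP Table 2, 0.7 v 0.3 per week with SD 0.45 and 0.3. Subject rates were gamma-distributed with variance SD² − mean/4, gaps exponential, d = 1, and dosing complete.

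| Rule | 0.7/week | 0.3/week | Difference | Ratio |
|---|---|---|---|---|
| SAP | 10.9 | 19.0 | 8.1 | 1.74 |
| Mean of all gaps | 9.4 | 16.5 | 7.1 | 1.75 |
| Longest interval | 15.8 | 21.2 | 5.4 | 1.34 |

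Time spent in attacks lowers the simulated rate in the higher-rate arm to about 0.63/week at d = 1. A simpler check, with Poisson counts, random placement and d = 2, gives differences of 8.7 days (SAP) and 7.4 days (mean of all gaps), with ratios 17.82/9.16 = 1.95 and 15.47/8.06 = 1.92.

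**The case against.** The strongest reply is that for two or more attacks the gaps between attacks are exactly what the label says, and end gaps are not between attacks. The dropped information is also partly reported elsewhere: time to first attack after first and after last dose by Kaplan-Meier, attack-free days and attack-free subjects. That is fair, but it does not explain why an end gap is used at one attack and the whole period at none. Those two rules are what break the label.

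Three stronger readings are tempting and are not supported.

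- **A second attack always costs more than half the score.** This is an average under random placement. For individual subjects the cut exceeds half in 58% (d = 0) to 74% (d = 5) of placements. It can be zero: with d = 2, one attack starting at day 24 scores 24 days, and so do two starting at days 0 and 26.
- **The rule inflates the treatment effect.** The longest interval is a maximum and compresses contrasts by nature. Against the mean of all gaps, the closest uniform rule, the ratio is practically unchanged and the difference rises by about 1 day. Pooling intervals gives a ratio of about 2.1, but the SAP does not state pooling, and that figure cannot be set against a measure with one value per subject.
- **Placebo subjects fall under one formula and treated subjects under another.** At 0.7 v 0.3/week, 73% of placebo subjects have two or more attacks and 69% of treated subjects have none or one. The interim results in Protocol 5.3.3.3 imply 0.898 − 0.384 = 0.514/week at 350 mg and 0.898 − 0.417 = 0.481 at 250 mg. With Poisson counts, 61% and 57% of those subjects would have two or more attacks. The split is plausible only near the 125 mg rate of 0.898 − 0.579 = 0.319.

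**Conclusion.** The point holds as a minor one. The interval is defined in three ways according to attack count, the table does not measure one quantity, and subjects can be ranked in the wrong order. That much follows from the SAP text without any assumption.

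The sizes do rest on assumptions: attack length, random placement, complete dosing and averaging within subject. Under them the mean score falls by 56% to 65% from one attack to two, clearly more than under either uniform rule over the same range of attack lengths. With evenly spaced attacks the fall is 33% to 48%. The effect on the difference between arms is about 1 day against the mean of all gaps and 2.7 days (8.1 − 5.4) against the longest interval.

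The primary attack rate and its ANCOVA in SAP 12.1.1 do not use this derivation and are not affected.

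**What to change.** In SAP 12.1.4, replace the three rules by one definition for every attack count, with one value per subject. It should include first dose to first attack, every gap between attacks, and end of last attack to end of the treatment period. The longest attack-free interval is one suitable choice. If gap lengths themselves are wanted, analyse all gaps from first dose as recurrent gap times, with the last gap right-censored at the end of the period. The SAP already censors attack-free subjects at last dose for time to first attack, so this fits its methods. State the level of summary for Table 14.2.3.1.1 and what a subject with no attack contributes when dosing stops before Day 28.

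SAP 11.3 allows computational algorithms to be refined. The cost is a few lines of text and reprogramming one descriptive table. No new data are needed. The displayed difference between arms may become smaller.

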- n Subjects will be randomized by the Sponsor on or after the screening visit and is contingent upon review of screening visit data entered into the eCRF subsequent questions the Sponsor may have. Randomization will trigger shipment of a kit of study drug for the first 14 days and an automatic resupply to arrive on-site at approximately study Day 10 after entry into the eCRF system that the subject has had a Day 1 visit. More details on randomization and kit shipment will be provided to the site.
- o The Investigator (or designee) will provide a diary for collection of HAE attacks (screening through follow-up) and study drug dosing (Days 1-28) at screening, Day 1, Day 14 and Day 29. Diaries will be collected on Day 1 (screening diary), Day 14, Day 29 and follow-up. At each visit and phone call, the Investigator (or designee) will review proper recording of attacks and dosing (as applicable) in the diary.
- p At any time the diary is in a subject's possession, they will enter HAE attacks and relevant details and dosing information (as applicable) at least once per day.
- q On Day 14, a blood sample for plasma PK and plasma kallikrein analysis will be drawn prior to dosing ( $< 5$  min) and at 1, 2, 3, 4, 5, 6, 8, and 24 hours postdose (i.e., on Day 15); Day 29 will be trough samples. If the subject is unable to provide serial PK samples on Day 14, steady state PK samples may be obtained on Day 28, with a 24-hour PK sample drawn at the scheduled visit on Day 29. In this case, trough PK samples will be drawn on Day 14. If the subject has a Day 29 visit for the 24-hour PK sampling, concomitant medications and AEs should also be assessed at the visit. Within 6 hours postdose, an acceptable window around each PK draw is  $\pm 10$  minutes. After 6 hours, an acceptable window is  $\pm 20$  minutes. Plasma PK and plasma kallikrein samples will be collected prior to in clinic dosing on Day 1 and Day 14. The Day 29 samples will be collected approximately 24 hours post-last dose.
- r Cleaved HK and an additional sample for possible exploratory analysis used to elucidate PD properties of BCX7353 will be drawn.
- s Subjects will take their study drug in the clinic on Day 1, Day 14 and Day 15 (Day 28 if subjects must complete serial PK on the last dose). Subjects will take all other doses at home as instructed. The last day of study drug dosing is Day 28.

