#### **10.6. Treatment Period For Efficacy Analyses**

There are 2 treatment periods for efficacy analyses.

1. The entire dosing interval (Days 1 to 28 inclusive) is the date of first dose to the last dose on day 28+24hours, or 24 hour post last dose of the study drug, whichever is earlier.
2. The steady-state or effective dosing interval (Days 8 to 28 inclusive) is the date of first dose +7 days to the last dose on day 28+24hours, or 24 hour post last dose of the study drug, whichever is earlier.

HAE attacks that occur during the treatment period will be included in all relevant efficacy data summaries.

HAE attacks that occur prior to or after the treatment period will also be summarized for the following periods: Qualification Period, screening to baseline Period and the follow-up period.

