### 10.8.1. Rate of Attacks

The primary endpoint, confirmed attack rate, is the total number of (count) confirmed attacks during the treatment period and standardized to an appropriate denominator, e.g. 7 days for a weekly attack rate. The weekly attack rate will be calculated for each subject:

$$\text{Weekly Attack Rate} = \frac{\text{Number of Attacks} * 7}{\text{Duration (days)}}$$

Number of attacks is total count of attacks reported during the respective dosing period (“Duration (days)” in the above equation]. The primary endpoint will be calculated for the entire dosing period and for the effective dosing period. The weekly attack rate will also be derived for all subject reported attacks and for confirmed attacks requiring treatment.

The attack rates will also be calculated for pre and post treatment periods:

Attack Rate from Screening to Baseline:

$$= \frac{\text{Total Number of attacks reported} * 7}{\text{Duration of the reporting period in days}}$$

Attacks with a start date after screening and before the date of first dose will be included and the duration of the reporting period is date of first dose – date of screening visit+1.

Attack Rate from date of day 29 to the last follow-up on study:

$$\frac{\text{Total Number of attacks reported} * 7}{\text{Duration of the reporting period period in days}}$$

Attacks that start greater than 24 hours after the last dose will be included. The duration of the reporting period is from the date of last dose+24 hours to the date of last follow-up.

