14.2.2.2	Summary of Rate of Confirmed Attacks during Effective Dosing Period (include the difference from qualifying on the same table)	FAS/PP
14.2.2.3	Summary of Number of Confirmed Attacks by Week during Effective Dosing Period	FAS/PP
14.2.2.4	Summary of Rate of Confirmed Attacks Requiring Treatment during Effective Dosing Period	FAS/PP
14.2.2.5	Summary of Rate of Confirmed Abdominal Attacks during Effective Dosing	FAS/PP

Tables	Title	Population
	Period	
14.2.2.6	Summary of Rate of Confirmed Peripheral Attacks during Effective Dosing Period	FAS/PP
14.2.2.7	Summary of Rate of Subject-Reported Attacks during Effective Dosing Period	FAS/PP
14.2.2.8	Statistical Analysis of Rate of Confirmed Attacks during Effective Dosing Period	FAS/PP
14.2.2.9	Statistical Analysis of Rate of Confirmed Attacks during Effective Dosing Period - Poisson-regression Model	FAS/PP
14.2.2.10	Statistical Analysis of Rate of Confirmed Attacks Requiring Treatment during Effective Dosing Period	FAS/PP
14.2.2.11	Sensitivity Statistical Analysis of Rate of Confirmed Attacks Excluding Missing Diary Days during Effective Dosing Period	FAS/PP
14.2.2.12	Sensitivity Statistical Analysis of Rate of Confirmed Attacks during Effective Dosing Period (BOCF)	FAS/PP
14.2.2.13	Statistical Analysis of Rate of Confirmed Abdominal Attacks during Effective Dosing Period	FAS/PP
14.2.2.14	Statistical Analysis of Rate of Confirmed Peripheral Attacks during Effective Dosing Period	FAS/PP
14.2.2.15	Statistical Analysis of Rate of Subject-Reported Attacks during Effective Dosing Period (subject reported qualifying rate will be used as covariate)	FAS/PP
14.2.2.16	Summary of Proportion of Subjects who are Attack-free during Effective Dosing Period (include sensitivity analyses of missing=failure; missing=excluded )	FAS/PP
14.2.2.17	Summary of Number of Attack-free days during Effective Dosing Period	FAS/PP
14.2.2.18	Summary of Percent of Attack-free days during Effective Dosing Period	FAS/PP
14.2.2.19	Statistical Analysis of Number of Attack-free days during Effective Dosing Period	FAS/PP
14.2.2.20	Statistical Analysis of Percent of Attack-free days during Effective Dosing Period	FAS/PP
14.2.2.21	Assessment of Dose Response - Effective Dosing Period	FAS/PP
The following will be provided for the Entire Dosing Period		
All tables will be repeated for the PP population		
Table Numbering: FAS tables will end as .1; PP tables will end as .2		

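### Time to first attack (SAP 12.1.4): attack-free subjects are censored at last dose while attacks count for up to 24 h more, so a first attack in that window drops the Kaplan-Meier curve too far (minor)

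*SAP*

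**What the plan says.** SAP 12.1.4 lists time to first attack after first study medication among its additional efficacy analyses. It asks for a Kaplan-Meier curve with median, quartiles and Brookmeyer-Crowley intervals. The censoring rule is: "Subjects who do not have an attack will be censored at the date of last dose for the KM analysis". The section gives no end date for events.

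SAP 10.6 runs the entire dosing interval to 24 h after the Day 28 dose "or 24 hour post last dose of the study drug, whichever is earlier". It adds: "HAE attacks that occur during the treatment period will be included in all relevant efficacy data summaries". SAP 10.8.1 places the boundary of the post-treatment rate at the same point: "Attacks that start greater than 24 hours after the last dose will be included".

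SAP 16 lists the output (Table 14.2.3.19) under the line "The following will be provided for the Entire Dosing Period". The curve itself is Figure 14.2.1.12. The schedule in SAP Table 1 fixes the usual censoring day: "The last day of study drug dosing is Day 28".

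The neighbouring analysis, time to first attack after the last dose, censors at the last follow-up assessment, which is the end of its own observation.

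**The concern.** Events and censoring have different end points. An attack 20 h after the Day 28 dose lies inside the SAP 10.6 interval and is an event. A subject who kept a diary and had no attack over the same hours has already left the risk set at last dose. These subjects are still observed, because SAP section 3 keeps the attack diary running to the follow-up visit. Observed attack-free time is therefore discarded only for those without an event, so censoring depends on the outcome.

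Completers share a last dosing day, so most attack-free subjects in an arm leave together. A first attack after that point may face a risk set of one.

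At stake are the tail of the curve and the median and third quartile read from it. The arms most exposed are those with many attack-free subjects, where the plateau is the result of interest. The curve could then disagree with the trial's own attack-free proportion.

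**Working it through.** The plan states no sample size, event count or power for this endpoint, so there is no figure to reproduce. The check has two parts: what the rule does when a late first attack occurs, and how often one occurs.

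**1. Effect of one late attack.** The estimator is S(t) = ∏(1 − d/r), with d events among r at risk. Take an arm of 18 (36 subjects in Part 1, randomised 1:1). One first attack falls on Day 29, within 24 h of the Day 28 dose. All attack-free subjects are censored on Day 28.

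| Attack-free | S before | SAP rule: r, S after | Censored at window end: r, S after |
|---|---|---|---|
| 13 of 18 | 14/18 = 0.778 | 1, 0 | 14, 13/18 = 0.722 |
| 9 of 18 | 10/18 = 0.556 | 1, 0 | 10, 9/18 = 0.500 |
| 6 of 18 | 7/18 = 0.389 | 1, 0 | 7, 6/18 = 0.333 |

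In the first row the SAP rule prints both median and third quartile as Day 29; with aligned censoring neither is reached. In the other two rows the third quartile is printed as Day 29 but is not reached.

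Two boundary cases limit the effect:
- If time is kept in whole dates and the attack is on Day 28 itself, it ties with censoring. Events are taken first and the step is correct.
- If one attack-free subject has a later last dose, then r = 2. With 9 attack-free, S goes from 0.556 to 0.278 instead of 0.500: too low, but not zero.

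**2. How often.** Inputs from SAP section 5 and Table 2: active mean 0.3/week, SD 0.3 or 0.4, n = 18. Assumptions: each subject has a constant attack rate, rates vary between subjects as a gamma distribution, all 28 daily doses are taken, and nobody drops out.

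Over 4 weeks the variance of an observed weekly rate is Var(λ) + mean/4, so Var(λ) = SD² − 0.3/4. With shape k = mean²/Var(λ) and scale θ = Var(λ)/mean, the probability of no attack by day t after first dose is S(t) = (1 + θt/7)^(−k).

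- SD 0.3: Var = 0.09 − 0.075 = 0.015, k = 6, θ = 0.05, S(28) = 1.2^(−6) = 0.335.
- SD 0.4: Var = 0.16 − 0.075 = 0.085, k = 1.059, θ = 0.2833, S(28) = 0.448.

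So 34–45% are truly attack-free. Without dropout, a single late first attack takes the curve to 0. The chance for an arm is 1 − (1 − p)^18, with p the chance that a subject's first attack falls in the affected window.

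- *Clock times* (censored at the Day 28 dose, t = 27): p = 0.3471 − 0.3349 = 0.0122, or 0.4575 − 0.4483 = 0.0092. The arm figure is 20% or 15%.
- *Whole dates* (dose assumed 9 h after midnight, so only Day 29 up to 9 h is affected, from t = 27 + 15/24 = 27.625): p = 0.3394 − 0.3349 = 0.0045, or 0.4517 − 0.4483 = 0.0034. The arm figure is 8% or 6%.

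Simulation of 3,000 arms per scenario under the same model gave 16–19% on clock times and 6–7% on whole dates, which agrees within simulation error. On clock times, a third quartile that was not reached was printed in 14–15% of simulated arms.

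With aligned censoring, the curve ends at 0 only if all 18 have an attack: at most (1 − 0.335)^18 = 0.0006.

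**The case against.** Four objections have weight.

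*The affected window is narrow.* SAP 10.6 takes the earlier of two limits, so it is at most 24 h. The censoring rule names a date, not a clock time, so the whole-date figure is closer to the text. This stands, and it is why 6–7% leads.

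*SAP 10.8 may remove the mismatch.* Its duration formula for the entire dosing period ends on the date of last dose. A programmer who cut events there would have no fault. But that formula sets the denominator of a rate. SAP 10.6 says which attacks count, and it keeps those in the 24 h after the last dose. The formula therefore does not cure the conflict, though the intent could be clearer.

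*The analysis carries little weight.* It is absent from the secondary endpoints of the protocol (7.2.2) and SAP (2.2.2) and from the comparisons in SAP 7.2. No log-rank test is planned, and protocol 13.2.4 states that there are no formal hypotheses. The attack-free proportion is derived directly under three discontinuation rules (SAP 10.8.2) and tested with Fisher's exact test. This stands and sets the severity.

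*The effect is conditional.* A reader might infer that the curve always falls to zero. It does so only when a first attack falls after every attack-free subject in that arm has been censored. For early discontinuers the bias is small because others remain at risk.

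A reader might also infer, since SAP 12.1.4 sets no end to the event window, that attacks through Day 44 count as events, which would make the fault far larger. The documents do not support this. The table stands under the entire dosing period, attacks more than 24 h after last dose belong to the post-treatment period, and a separate Kaplan-Meier analysis covers time after the last dose.

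**Conclusion.** The concern holds as a minor one. The event window and the censoring rule do not end together, and the arithmetic follows from the text. When a first attack falls in the gap, the curve drops too far, to 0% if no attack-free subject in that arm has a later last dose. A median or third quartile can then be reported that was not reached.

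Under the planning values, a false 0% occurs in about 6–7% of arms on whole dates (closed form 6–8%) and 16–19% on clock times (closed form 15–20%), against about 0% with aligned censoring. These figures assume 18 subjects per arm, 0.3 attacks/week with SD 0.3–0.4, gamma-distributed subject rates and no dropout. The whole-date figure also assumes dosing at 9 h. The documents do not say which time scale will be programmed.

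The primary attack-rate analysis and the attack-free proportion are not affected.

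**What to change.** In SAP 12.1.4, define the event as the first confirmed attack with onset from first dose to the end of the SAP 10.6 entire dosing interval. Censor subjects without such an attack at the end of that same interval, or at the last completed diary entry if earlier. State one time scale, either date and time or whole dates, for both events and censoring.

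The cost is a sentence or two in the SAP and one changed censoring variable for Table 14.2.3.19 and Figure 14.2.1.12. No new data are needed, because the diary already covers the extra hours, and no other analysis changes.
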